6.2 Subgroups

The following subgroups will be considered for the study based on baseline LVEF (%):

- HFrEF subgroup defined as all patients with LVEF \leq 45 % at baseline;
- HFpEF subgroup defined as all patients with LVEF $>$ 45 % at baseline.

Unless otherwise specified all summaries will be stratified by the subgroups: HFrEF, HFpEF and Overall.

7 ANALYSIS METHODS

7.1 Disposition

Disposition will be summarized descriptively using counts and percentages for the All Enrolled population by subgroup and overall. The number and percentage of patients screened, screen failures, patients with Aortix Pump implanted and completed the study will be presented, together with number and percentage of patients who prematurely discontinued from the study along with reasons for study discontinuation will be summarized.

A listing of patient's disposition status will be provided. The number of patients in each analysis population will be summarized descriptively with counts and percentages separately. A listing of patient's inclusion to analysis sets will be provided. A patient's eligibility with inclusion/exclusion criteria completions or violations will be listed. Disposition tree plot will be provided associated with corresponding table.

7.2 Demography and Baseline Characteristics

Demographic data and baseline characteristics will include:

- Sex;
- Ethnicity;
- Race;
- Age (years);
- LVEF (%);

- Height (cm);
- Weight (kg);
- Body Mass Index (BMI) (kg/m²).

Demographics and baseline characteristics will be summarized descriptively by subgroup and overall. Summary statistics including number of patients, mean and standard deviation, median, minimum, and maximum will be generated for all continuous variables such as age, LVEF, height, weight, and BMI. The number and percentage of patients within each category will be presented for all categorical variables such as sex, race, and ethnicity. The summary results will be reported on the ITT and As-Treated populations.

Demographic data and baseline characteristics will be listed for the ITT population with stratification by As-Treated population.

7.3 Medical History

Medical history will be summarized with descriptive statistics by categories for ITT and As-Treated populations by subgroup and overall.

Medical history will be listed for ITT population with stratification based on patient's inclusion into As-Treated population.

7.4 Medications

Summary of medications by category will be provided with descriptive statistics for ITT and As-Treated populations by subgroup and overall.

Doses of Inotropes and Diuretics will be summarized with descriptive statistics for As-Treated population by Timepoint (Baseline Monitoring, Day of Implant, Congestion Target Met, Post 72Hrs or Discharge and Follow-Up).

Listings of medications for ITT population will be provided with stratification based on patient's inclusion into As-Treated population.

7.4.1 Baseline Medications

Baseline medication will be defined as any medication received within 48 hours prior to the start of Aortix treatment. Summary of baseline medications by category will be provided with descriptive statistics for As-Treated populations by subgroup and overall for the following medication categories:

- ACE Inhibitor
- ARNI

- Angiotensin Receptor Blocker
- Beta Blocker
- Diuretic
- Inotrope

In case when start/stop date is incomplete, or medication is ongoing, the following assumption will be made for Baseline medication classification:

- If there is a reasonable possibility that medication was taken within 48 hours prior to the start of Aortix treatment the medication will be considered as Baseline medication;
- If there is no evidence that medication was taken within 48 hours prior to the start of Aortix treatment the medication will not be classified as Baseline medication.

7.4.2 Loop Diuretic – Analysis of Furosemide Equivalents

There will be 2 analysis periods defined:

- Baseline analysis period – from 48 prior to the start of Aortix treatment until the start of Aortix treatment.
- Aortix Treatment analysis period – from the start of Aortix treatment until the end of Aortix treatment.

For the pre-specified list of loop diuretics (which are defined by Medication Memo) an average daily dose of corresponding medication received during the specified analysis period will be derived for the Baseline analysis period and Aortix Treatment analysis period. In cases when start/stop date is incomplete the maximum possible duration of medication treatment will be used for derivation of the average daily dose.

An average daily dose of each specified medication will be converted to furosemide equivalents (per Medication Memo) and the Total Average Daily Dose of Furosemide Equivalents (mg) will be derived as the sum of all converted average daily doses. If there are no diuretics received from a pre-specified list of loop diuretics (which are defined by Medication Memo) during the analysis period (Baseline or Aortix Treatment) then the Total Average Daily Dose of Furosemide Equivalents will be set to 0.

Summary of Total Average Daily Dose of Furosemide Equivalents (mg) at Baseline analysis period and Aortix Treatment analysis period will be provided along with the summary of change from Baseline analysis period to Aortix Treatment analysis period.

Specified derivations and analysis will be conducted only for the Diuretic Equivalents Analysis population.

The list of medications will correspond to the latest version of Medication Memo.

7.4.3 Analysis of Inotropes Dosing Stages

There will be 2 analysis periods defined:

- Baseline analysis period – from 48 prior to the start of Aortix treatment until the start of Aortix treatment.
- Aortix Treatment analysis period – from the start of Aortix treatment until the end of Aortix treatment.

For the pre-specified list of inotropes (which are defined by Medication Memo) an average daily dose of corresponding medication received during the specified analysis period will be derived for the Baseline analysis period and Aortix Treatment analysis period. In cases when start/stop date is incomplete the maximum possible duration of medication treatment will be used for derivation of the average daily dose.

For each analysis period, inotropes will be categorized into stages based on the average daily dose according to the stages table (which is defined by Medication Memo).

Summary of inotropes dosing stages and a proportion of patients with Decreased Stage, Increased Stage and Not Changed will be provided with descriptive statistics by medications category (which are defined by Medication Memo) for As-Treated populations by subgroup and overall.

The list of medications will correspond to the latest version of Medication Memo.

7.5 Protocol Deviations

A listing of protocol deviations will be presented by patient for the All Enrolled population.

7.6 Pump Speed Changes

Pump speed changes will be reported for the PSC population.

7.7 Aortix Pump Deployment/Retrieval Procedure

Aortix Pump Deployment Procedure analysis will include:

- Time from Skin Break to Pump Placement (min)
- Time from Skin Break to delivery Sheath Insertion (min)
- Time from Aortix Pump Final Placement to Hemostasis Achieved (min)
- Questions for Physician Who Performed Aortix Pump Deployment using the ADS
 - Is visibility of system adequate?
 - Is force required to unsheathe Aortix Pump from Delivery Sheath acceptable?

- Is visibility of delivery sheath tip adequate?
- Was overall time to place Aortix Pump acceptable?

Aortix Pump Retrieval Procedure analysis will include:

- Time from Broke Hemostasis at Access Site to Vessel re-access with ARS (min)
- Time from Broke Hemostasis to time Hemostasis Achieved (min)
- Type of Closure Devices used
- Questions for Physician Who Performed Retrieval using the ARS
 - Is visibility of support catheter adequate?
 - Visibility of Retrieval Sheath and Dilator
 - Is force required to re-sheath Aortix Pump acceptable?

Aortix Pump Deployment/Retrieval Procedure parameters will be summarized descriptively by subgroup and overall. Summary statistics including the number of patients, mean and standard deviation, median, minimum, and maximum will be generated for all continuous variables such as Time (min). The number and percentage of patients within each category will be presented for all categorical variables such as Type of Closure Devices used and Questions for Physician Who Performed Retrieval using the ARS. The summary results will be reported based on the As-Treated population.

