6.1.2 Intent-to-Treat (ITT) Population

The ITT population will be defined as all enrolled patients that have an attempted implant whether or not successful. This population will be used for demographic and partial safety analyses.

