6.1.3 As-Treated Population

The As-Treated population will be defined as all enrolled patients with the pump implanted (hemostasis achieved). This population will be used for partial demographic analysis as well as all safety and efficacy analyses.

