7.8.2 Device Performance

A Device Performance analysis will be performed for ITT or As-Treated population to include:

- Deployment success defined as total number of patients with a successfully implanted Aortix Pump compared to the total number of patients within ITT population.
- Retrieval success defined as total number of patients with a successfully retrieved Aortix Pump compared to the total number of patients within the As-Treated population.
- Percentage of patients with ADS, ARS and pump device-related adverse events defined as the total number of patients with CEC-classified AEs of the corresponding category from the time of implant procedure through 30 days post-implant Follow-Up compared to the total number of patients in either the ITT population or As-Treated population as appropriate.

Descriptive summary will be provided for variables within Device Performance analysis. Corresponding listing will be provided for ITT population.

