8 APPENDIX

Appendix 1: List of Tables, Figures and Listings

Table Number	Table Title
14.1.1.1	Summary of Patient Disposition (All Enrolled)
14.1.1.2	Summary of Analysis Populations (All Enrolled)
14.1.2.1	Summary of Demographic and Baseline Characteristics (Intent-to-Treat Population)
14.1.2.2	Summary of Demographic and Baseline Characteristics (As-Treated Population)
14.1.3.1	Summary of Medications (Intent-to-Treat Population)
14.1.3.2	Summary of Medications (As-Treated Population)
14.1.3.3	Summary of Baseline Medications (As-Treated Population)
14.1.3.4	Summary of Furosemide Equivalents (Diuretic Equivalents Analysis Population)
14.1.3.5	Summary of Inotropes Dosing Stages (As-Treated Population)
14.1.4.1	Summary of Medical History (Intent-to-Treat Population)
14.1.4.2	Summary of Medical History (As-Treated Population)
14.1.5.1	Summary of Aortix Pump Deployment Procedure (As-Treated Population)
14.1.5.2	Summary of Aortix Pump Retrieval Procedure (As-Treated Population)
14.2.1.1	Summary of Primary Safety (As-Treated Population)
14.2.1.2	Summary of Device Performance (Intent-to-Treat Population)
14.2.1.3.1	Summary of Primary Effectiveness – General Summary (As-Treated Population)
14.2.1.3.2	Summary of Primary Effectiveness – Effectiveness Measurements Comparing (As-Treated Population)
14.2.1.3.3	Summary of Primary Effectiveness - Hourly Rate of Fluid Intake/ Urine Output/ Net Loss (As-Treated Population)
14.3.1.1.1	Summary of CEC-classified Adverse Events (Intent-to-Treat Population)
14.3.1.1.2	Summary of Investigator-classified Adverse Events (Intent-to-Treat Population)
14.3.1.2	Summary of CEC-classified Treatment-Emergent Adverse Events (Intent-to-Treat Population)
14.3.1.3	Summary of CEC-classified Treatment-Emergent Adverse Events by Relationship (Intent-to-Treat Population)
14.3.1.4	Summary of CEC-classified Serious Adverse Events (Intent-to-Treat Population)
14.3.1.5	Summary of CEC-classified Unanticipated Adverse Device Effect (Intent-to-Treat Population)
14.3.2	Summary of CEC-classified Deaths During the Study (Intent-to-Treat Population)
14.3.4.1.1	Summary of Blood Labs (As-Treated Population)
14.3.4.1.2	Summary of Blood Labs (Pump Speed Changes Population)
14.3.4.2.1	Summary of Urine Labs (As-Treated Population)

Table Number	Table Title
14.3.4.2.2	Summary of Urine Labs (Pump Speed Changes Population)
14.3.4.3.1	Summary of Lactate Dehydrogenase, Plasma Free Hb and Urine Hemoglobin (As-Treated Population)

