14.3.7.3	Boxplots of KCCQ Scores (As-Treated Population)
14.3.8.2	Boxplots of Dyspnea Score (As-Treated Population)

Listing Number	Listing Title
16.2.1.1	Listing of Screen Failure and Inclusion / Exclusion Criteria Assessment (All Enrolled)
16.2.1.2	Listing of Patient Disposition (All Enrolled)
16.2.2	Listing of Protocol Deviations (All Enrolled)
16.2.3	Listing of Analysis Populations (All Enrolled)
16.2.4.1	Listing of Patient Demographic and Baseline Characteristics (Intent-to-Treat Population)
16.2.4.2	Listing of Medical history (Intent-to-Treat Population)
16.2.4.3	Listing of Medications (Intent-to-Treat Population)
16.2.4.4	Listing of Furosemide Equivalents - Average Daily Dose (Diuretic Equivalents Analysis Population)
16.2.4.5	Listing of Inotropes Dosing Stages - Average Daily Dose (As-Treated Population)
16.2.5.1	Listing of Aortix Implant Procedure (Intent-to-Treat Population)
16.2.5.2	Listing of Aortix Retrieval Procedure (As-Treated Population)
16.2.5.3	Listing of Pump Speed Changes (Pump Speed Changes Population)
16.2.5.4	Listing of Device Deficiency (As-Treated Population)
16.2.6.1	Listing of Primary Safety (As-Treated Population)
16.2.6.2	Listing of Device Performance (Intent-to-Treat Population)
16.2.6.3	Listing of Primary Effectiveness (As-Treated Population)
16.2.6.4	Listing of Congestion Target (As-Treated Population)
16.2.7.1	Listing of CEC-classified Adverse Events (All Enrolled)
16.2.7.2	Listing of Investigator-classified Adverse Events (All Enrolled)
16.2.8.1	Listing of Urine Chemistry (As-Treated Population)
16.2.8.2	Listing of Blood Labs (As-Treated Population)
16.2.9	Listing of Vital Signs (As-Treated Population)
16.2.10.1	Listing of NYHA Classification (As-Treated Population)
16.2.10.2	Listing of Hemodynamics (As-Treated Population)
16.2.10.3	Listing of Cardiovascular Exam (As-Treated Population)
16.2.10.4	Listing of Echo (As-Treated Population)
16.2.10.5	Listing of Cardiac Output and Cardiac Power Output (As-Treated Population)
16.2.11.1	Listing of Dyspnea Evaluation (As-Treated Population)
16.2.11.2.1	Listing of Fluid Intake/ Urine Output (As-Treated Population)
16.2.11.2.2	Listing of Cumulative Fluid Intake, Urine Output and Net Loss (As-Treated Population)
16.2.11.2.3	Listing of Hourly rate of Fluid Intake / Urine Output / Net Loss (As-Treated Population)
16.2.12.1	Listing of EQ5D (As-Treated Population)
16.2.12.2	Listing of KCCQ (As-Treated Population)
16.2.13.1	Listing of Follow-up Information (As-Treated Population)

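### The operator ratings of the delivery system and the deployment times are summarised only in implanted patients, so ratings from failed attempts enter no summary table and the percentages could look more favourable than over all attempts

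*SAP*

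**What the plan says.** SAP 7.7 lists three deployment intervals: skin break to pump placement, skin break to delivery sheath insertion, and final placement to hemostasis. It also lists four items under "Questions for Physician Who Performed Aortix Pump Deployment using the ADS": visibility of the system, force to unsheathe the pump, visibility of the sheath tip, and acceptability of the overall placement time. Retrieval items follow. For all of them, "The summary results will be reported based on the As-Treated population".

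The two populations that matter are defined in SAP 6.1:
- ITT (6.1.2): "The ITT population will be defined as all enrolled patients that have an attempted implant whether or not successful".
- As-Treated (6.1.3): "The As-Treated population will be defined as all enrolled patients with the pump implanted (hemostasis achieved".

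Elsewhere the same procedure is handled in ITT. SAP 7.8.2 has "Deployment success defined as total number of patients with a successfully implanted Aortix Pump compared to the total number of patients within ITT population", reported in Table 14.2.1.2. In Appendix 1, Listing 16.2.5.1 covers the implant procedure in ITT, while Table 14.1.5.1 summarises the deployment procedure in As-Treated. The table list contains no ITT version of Table 14.1.5.1.

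**The concern.** Membership of the As-Treated population depends on the outcome that these questions help to explain. If a pump could not be seen, unsheathed or placed, that operator's answers on visibility and force are among the most informative in the study, yet they contribute to no percentage.

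Failed attempts are foreseen. Both documents name inability to implant as one reason for not receiving the pump (Protocol 7, SAP 2.3), and Protocol 4.8 sets separate follow-up for patients with an attempted but unsuccessful implant. The first performance objective is delivery with the Aortix Delivery System, and the results are meant to inform the design of later studies. A designer who takes the ratings from Table 14.1.5.1 would be reading figures conditional on success.

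The restriction is not a general convention of the SAP either. Demographics, medical history and medications (7.2 to 7.4) are summarised in both populations.

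**Working it through.** **The plan's own figure.** The only related number is the enrolment target. SAP 2.3 expects about 50% of enrolled patients not to receive the pump: 30 / (1 − 0.50) = 60, which reproduces its figure. Protocol 7 gives 33% for the same target: 30 / (1 − 0.33) = 44.8, or 45, which does not give 60. That inconsistency is separate, and nothing here depends on it. Neither percentage separates failed attempts from screening exclusions, so the number of failed attempts cannot be derived from the documents.

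**Which items can exist for a failed attempt.**

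| SAP 7.7 item | Defined if no pump is placed? |
|---|---|
| System visibility; sheath-tip visibility | Yes, if the operator answers |
| Unsheathing force | Yes, if unsheathing was tried |
| Acceptability of overall placement time | Doubtful; presumes placement |
| Skin break to sheath insertion | Yes, if the sheath went in |
| Skin break to pump placement | Only if placement was reached |
| "Time from Aortix Pump Final Placement to Hemostasis Achieved (min" | No |
| Retrieval items | No |

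The point therefore applies mainly to the visibility and force ratings and the time to sheath insertion.

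**Size.** Let 30 be the planned implants (SAP 2.3), k the failed attempts with recorded ratings, p the favourable proportion among implants and q that among failures.

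- As-Treated percentage = p
- ITT percentage = (30p + kq) / (30 + k)
- Gap = k / (30 + k) × (p − q)

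The documents give neither k, p nor q. Assume k from 0 to 4, and take the extreme p = 1, q = 0:

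| k | As-Treated | ITT | Gap (points) |
|---|---|---|---|
| 0 | 100% | 30/30 = 100% | 0 |
| 1 | 100% | 30/31 = 96.8% | 3.2 |
| 2 | 100% | 30/32 = 93.75% | 6.25 |
| 3 | 100% | 30/33 = 90.9% | 9.1 |
| 4 | 100% | 30/34 = 88.2% | 11.8 |

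These are upper bounds for each k. If q = p, the gap is 0 for every k. If 27 of 30 implants are rated favourably (90.0%) and k = 3, the ITT figure lies between 27/33 = 81.8% (all failures unfavourable) and 30/33 = 90.9% (all favourable), so the gap runs from 8.2 points to −0.9 points. The ceiling moves with the assumed k: ten failures would give 30/40 = 75%, a gap of 25 points.

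**The case against.** The strongest reply is that the plan already shows failed deployments where delivery performance is an endpoint. Each failure lowers the ITT success rate, adverse events are summarised in ITT (SAP 7.9.1), the implant procedure is listed in ITT, and Protocol 7 says that each patient's data will be looked at individually. The SAP 7.7 items appear among neither the endpoints nor the additional data in Protocol 3.3 or SAP 5, and the table title names its population. All of this stands, and it keeps the point small. It does not supply a summary of the ratings over all attempts. The device deficiency listing (16.2.5.4) does not help, because it is also As-Treated.

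A second reply is that a difficult deployment that ends in an implant keeps its poor ratings. Protocol 4.4.2 allows an unsatisfactory pump to be repositioned or replaced, so some troubled procedures will stay in As-Treated. This stands too. A reader might infer that the plan removes unfavourable answers by design; the documents do not support that. Only answers from attempts that never ended in an implant are lost, and such attempts may have failed for reasons unrelated to visibility or force.

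A third reply is that the questions may not be completed after a failed attempt. The case report form is not among the documents, and the title of Listing 16.2.5.1 does not name the questions. Under SAP 3.2, percentages use non-missing values by default, so with no answers recorded a change of population would leave the ratings unchanged. This is a genuine uncertainty about the gain.

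**Conclusion.** The population mismatch is confirmed from the definitions: deployment success is counted over all attempts, while the delivery-system ratings and deployment times are summarised only where the attempt succeeded. The percentages could therefore look more favourable than they would over all attempts.

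A reader might go further and conclude that delivery performance will look better than it was. The documents do not establish this. It needs at least one failed attempt, recorded ratings for it, and ratings worse than those of the implants, and none of the three is known. Under the assumption of 0 to 4 failed attempts beside 30 implants all rated favourably, the gap lies between 0 and about 12 points, the upper end being the worst case. Nor does the point extend to every deployment time, since placement-dependent intervals do not exist for a pump never placed. It concerns descriptive items outside the endpoints and is a low-priority improvement.

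**What to change.** In SAP 7.7 and Table 14.1.5.1:

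- Summarise the two visibility questions, the unsheathing-force question and the time from skin break to sheath insertion in ITT, split by implant success, with the number of patients with data in each column. Include the placement-time question where it was answered.
- Report skin break to pump placement only where placement was reached.
- Keep final placement to hemostasis and all retrieval items in As-Treated.
- Check that the case report form records the operator questions for failed attempts; the gain depends on it.

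The cost is a short change of wording and one revised table. It needs no extra patients, and no new missing-data rule, because SAP 3.2 already bases percentages on non-missing values. If the questions are already recorded for failed attempts, it needs no new data either. The ratings may come out slightly less favourable.

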7.8 Main Study Endpoints

7.8.1 Primary Safety

A Primary Safety analysis will be performed for the As-Treated population to include:

- Percentage of patients with Serious Adverse Events (SAE) defined as the total number of patients with a CEC-classified SAE from the time of enrollment through 30 days post-implant Follow-Up, compared to the total number of patients within the population. Patients with two or more CEC-classified SAE will be counted only once.
- Percentage of patients with Serious Procedure Related Adverse Events (SPRAE) defined as the total number of patients with CEC-classified SPRAE from the time of implant procedure through 30 days post-implant Follow-Up, compared to the total number of patients within the population. Patients with two or more CEC-classified SPRAE will be counted only once. Procedure Related Adverse Events will be defined as any AE related to Aortix Pump Deployment Procedure or Aortix Pump Retrieval Procedure.

Descriptive summaries will be provided for both Percentage of patients with SAE and Percentage of patients with SPRAE for As-Treated population. Corresponding listing will be provided for As-Treated Population.

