7.9 Safety and Additional Data Analysis

7.9.1 Adverse Events (AE)

CEC classification will be used for the analysis of AEs. Additional overall summary and listing for the Investigator's classification of AEs will be provided.

TEAEs will be defined as AEs not present prior to the start of study procedures, or AEs present before study treatment that worsened after implantation. If a partially missing date or time of onset allows the possibility that an AE may be a TEAE it will be presumed to be a TEAE.

AEs will be summarized by subgroup and overall by the number and percentage of patients who experienced at least one AE of any of the following types: any AE, any TEAE, any TEAE Related to Aortix Therapy, any TEAE Related to Aortix Procedure(Aortix Implant Procedure or Aortix Retrieval Procedure), any TEAE Related to Study Required Procedures, any serious TEAEs, any SAE, any SAE Related to Aortix Procedure, any SAE leading to death, any unanticipated adverse device effect.

AEs will be summarized by categories for the ITT population.

TEAEs will be summarized by category and by relationship for the ITT population.

Listings of all AEs will be provided for the All Enrolled population.

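### Both primary safety rates are computed only in successfully implanted patients, so a serious event in a failed implant attempt appears in the ITT adverse event tables but not in the primary rates

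*SAP*

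**What the plan says.** SAP 7.8.1 sets the population for both primary safety rates: "A Primary Safety analysis will be performed for the As-Treated population to include" the percentage of patients with an SAE and the percentage with an SPRAE. Table 14.2.1.1 and Listing 16.2.6.1 carry the same population. SAP 6.1.3 defines it: "The As-Treated population will be defined as all enrolled patients with the pump implanted (hemostasis achieved". It also says of that population: "This population will be used for partial demographic analysis as well as all safety and efficacy analyses".

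The SPRAE rate starts at the implant procedure, and SAP 7.8.1 specifies which events count: "Procedure Related Adverse Events will be defined as any AE related to Aortix Pump Deployment Procedure or Aortix Pump Retrieval Procedure".

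SAP 6.1.2 defines a separate ITT set of all attempted implants, successful or not. It is used for deployment success in 7.8.2 ("Deployment success defined as total number of patients with a successfully implanted Aortix Pump compared to the total number of patients within ITT population") and for the general adverse event tables, such as Table 14.3.1.1.1 ("Summary of CEC-classified Adverse Events (Intent-to-Treat Population"). The rows planned in 7.9.1 include "any SAE, any SAE Related to Aortix Procedure, any SAE leading to death".

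Protocol 3.3.1 defines the two primary safety endpoints by time frame only: from enrollment (SAE) or procedure (SPRAE) to the 30 day visit. It does not limit them to successful implants. Protocol 3.2 includes delivery of the pump in the safety objective. Protocol 4.8 follows failed attempts for adverse events for 30 days (±7) from the attempt, and implanted patients for 30 days (±7) from retrieval.

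**The concern.** An access-site or aortic injury can be the reason an implant is abandoned. When that happens, the injury itself removes the patient from the population in which procedural injuries are counted. On its literal wording, the hemostasis condition could also remove a patient whose pump was placed but who bled or died before hemostasis.

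Protocol section 6 gives a concrete case. A procedure-related aortic injury needing surgical repair pauses enrollment. If the same injury aborted the implant, it would not count in the primary SPRAE rate.

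What is at stake is how the headline figure is read. SAP 2.3 says that the study will inform the design of later studies. A reader who takes the rate labelled primary would not learn from 7.8.1 that failed attempts are left out, why, or where the figure for all attempts can be found. SAP 7.14, which lists changes from the protocol analyses, mentions only urine output.

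**Working it through.** **Who is counted.** Take a patient with an attempted implant, a serious deployment injury, and no pump implanted.

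- ITT (6.1.2): in.
- As-Treated (6.1.3): out.
- Deployment success (7.8.2, ITT): in the denominator, counted as a failure.
- Primary SAE and SPRAE rates (7.8.1, As-Treated): in neither numerator nor denominator.
- General adverse event tables 14.3.1.1.1, 14.3.1.3 and 14.3.1.4 (ITT): counted.
- Device performance, Table 14.2.1.2 ("Summary of Device Performance (Intent-to-Treat Population"): can be counted if the event is device-related.

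**The only related figure in the plan.** SAP 2.3 expects about 50% of enrolled patients not to receive the pump: 30/(1 − 0.50) = 60 enrolled, which reproduces its figure and leaves 60 − 30 = 30 not implanted. Protocol section 7 gives about 33%: 30/(1 − 0.33) = 44.8, or about 15 not implanted. Both totals include patients excluded on anatomy or hemodynamics, so they only bound the number of failed attempts. Neither document projects that number. The only implant record, in Protocol 1.2, is six patients with the pump deployed in all cases.

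**Illustration.** Let e be the implanted patients with an event, f the failed attempts, and g the failed attempts with an event. The As-Treated rate is e/30 and the ITT rate is (e + g)/(30 + f). All three counts are assumptions. For e, 2 and 5 come loosely from the large-bore complication range in Protocol 5.2: 30 × 5.9% = 1.8 and 30 × 15% = 4.5. The value 0 is added as the starkest case. Intervals are exact 95%.

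| As-Treated | f | g | ITT | Shift (points) |
|---|---|---|---|---|
| 0/30 = 0% (0 to 11.6%) | 1 | 1 | 1/31 = 3.2% | +3.2 |
| 2/30 = 6.7% (0.8 to 22.1%) | 1 | 1 | 3/31 = 9.7% | +3.0 |
| 2/30 = 6.7% | 5 | 1 | 3/35 = 8.6% | +1.9 |
| 5/30 = 16.7% (5.6 to 34.7%) | 1 | 1 | 6/31 = 19.4% | +2.7 |
| 5/30 = 16.7% | 5 | 0 | 5/35 = 14.3% | −2.4 |
| 5/30 = 16.7% | 10 | 1 | 6/40 = 15.0% | −1.7 |

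The ITT rate is the higher one only when g/f exceeds e/30. With g = 1 that means f below 30/2 = 15 when e = 2, and f below 30/5 = 6 when e = 5. Every shift shown lies well inside the As-Treated interval. More events among failed attempts would move the rate further: three failed attempts, all with events, take 0/30 to 3/33 = 9.1%.

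**The window.** SAP 7.8.1 closes both rates at a follow-up counted 30 days from implant. Protocol 4.8 counts 30 days (±7) from retrieval. With seven days of therapy (the duration for which Protocol 4.5 says the pump was tested), 30 days from retrieval is day 37 from implant. A failed attempt has no implant date, so the SAP's window gives it no starting point. Any ITT version of the rate must settle this.

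**The case against.** The strongest reply is that this concerns a label. The general adverse event tables are ITT and already plan percentages for any SAE and for any SAE related to the Aortix procedure, which closely match the two primary rates. The listings cover all enrolled patients. The study has no safety hypothesis or threshold, Protocol section 7 says each patient's data will be reviewed individually, and the enrollment pause operates whatever the analysis population. All of that stands and limits the impact. It does not explain why the rate labelled primary depends on procedural success.

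A second reply is that As-Treated contradicts no protocol text, because the protocol names no analysis population, and that failed attempts have neither therapy nor retrieval, so ITT is imperfect too. That is fair, and it is why As-Treated should be shown beside ITT. Also, Protocol 4.4.2 lets a pump be repositioned or replaced, so a first deployment that is rescued stays in As-Treated with its events.

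Several stronger readings are tempting, and the documents do not support them:

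- That SAP 7.8.2 follows a contradictory policy. Deployment success needs attempts in its denominator, and the same section uses As-Treated for retrieval success. It matches denominators to who is at risk.
- That the primary rate is necessarily too low. Failed attempts with few or no events would make the ITT rate the lower one.
- That the 5.9% to 15% range predicts the SPRAE rate. It describes major vascular access complications in valve-replacement trials, and 5/30 lies slightly above it.
- That an SAE rate in all enrolled patients is needed because the window opens at enrollment. Protocol section 6 collects events only once invasive or non-standard screening begins. Protocol 4.8 follows screened patients who never had an attempt for 7 days (±2) or to discharge, whichever is first.

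**Conclusion.** The point holds as a modest defect in the definition of the primary rates that should be fixed. A serious deployment-related event in an attempt that does not end in an implanted pump with hemostasis is absent from both primary safety rates. This matters most for the SPRAE rate, which is meant to count such events. That conclusion follows from the SAP's definitions alone.

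The size and direction are unknown. The shifts of about +3 and −2.4 points rest on 30 implanted patients and assumed counts of events and failed attempts. A reader might infer that serious events are hidden or that a formal safety decision is affected. Neither follows: the events stay in the ITT tables, and no decision rule uses the primary rates. What remains is that the report can carry two different rates for nearly the same quantity, with the one labelled primary excluding failed attempts and no reason given.

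**What to change.** - In SAP 7.8.1, Table 14.2.1.1 and Listing 16.2.6.1, report the SAE and SPRAE rates in ITT as primary, with As-Treated alongside.
- In the same edit, replace the post-implant window with the protocol's 30 day visit: 30 days (±7) from retrieval for implanted patients, and 30 days (±7) from the attempt for failed attempts. Footnote that failed attempts have no therapy or retrieval exposure.
- Amend 6.1.3 so that As-Treated is not assigned every safety analysis, since the adverse event tables are ITT.
- Align the death summary in 7.12 (As-Treated) with Table 14.3.2 and Listing 16.2.13.2 (both ITT).

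The cost is SAP wording plus one table and one listing rerun on a set already defined, with no new data. The headline rate may move slightly either way. ITT also mixes in patients with less exposure, which the As-Treated column makes visible. If the sponsor keeps As-Treated as the headline, the minimum is a stated reason in 7.8.1 and a cross-reference to Table 14.3.1.1.1.
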